## **A.2. Characterizing missing data**

We may be unable to track mother and child outcomes for pregnant women enrolled in our trial over the entire period spanning pregnancy and the child's first two years of life for various reasons. First, we may be unable to match the identifying information provided by women at study enrollment to administrative records because of poor data quality or because women enrolled in the trial moved out of state. Second, we may be unable to match women to their index birth because of problems linking mother and child records within South Carolina's administrative record system or because their pregnancy ended in pregnancy loss. We may be unable to observe child outcomes through 24 months if a child dies before reaching 24 months of age. For outcomes that can only be observed in Medicaid claims data, such as child preventative health outcomes and outpatient care utilization for mothers, we will not observe outcomes for mothers or children not enrolled in Medicaid. Whenever possible, we will report missing outcome data and characterize missing outcome data across each of these groups. More details are provided in Addendums 1-3 regarding plans to characterize missing outcome data related to each of the three domains of potential program impact and plans for sensitivity analyses to account for potential patterns in missing outcome data.

Because administrative records update continuously over time, we anticipate that mothers and babies classified as falling within our study sample definitions may change as administrative data is updated. For example, a mother enrolled in the trial whom we cannot initially match to any records may later match to state Medicaid records. Furthermore, administrative data may experience delayed reporting or data errors that are corrected later. We may revisit analyses several years after completion to assess the robustness of results to updated administrative records.

## **B. Analytical considerations**

### **B.1. Control variables**

In addition to reporting unadjusted models of program impact, we plan to report models that adjust for characteristics at baseline that may be associated with our primary academic outcomes. These include participant age, race and ethnicity, gestational age at study enrollment, relationship with the father of the child, education, employment, use of social services, housing stability, health care utilization, health behaviors and physical and mental health status all measured during the baseline survey. Specific variable definitions that we plan to include as control variables are specified below. Binary variables will be coded as "1", "0", or missing; for coding categorical variables, we will consider distributions across the control and treatment groups including missing values. We plan to use the same set of control variables in all analyses.

- Implementing Agency

- Indicators for each implementing agency enrolling study participants
- Demographics:
  - Indicator for age equal to 15, 16, or 17
  - Indicator for age equal to or greater than 28
  - Race – indicators for non-Hispanic Black, non-Hispanic white, other
  - Ethnicity – indicator for Hispanic/Latina
- Gestational age at time of study enrollment
  - A continuous variable of weeks to delivery as calculated by difference in estimated due date and the survey date
- Relationship with father of the child
  - Indicator for daily interaction with father of the child
- Education
  - Indicator for high school diploma or GED with no higher education
  - Indicator for less than high school diploma
- Employment, Income, and Financial Resources
  - Indicator for whether the mother is working for pay at the time of the survey
- Social services
  - Indicator for receiving one or more social service (i.e. TANF, SNAP, SSI, unemployment benefits, and WIC)
- Housing stability
  - Indicator for moving two or more times in the previous twelve months
  - Indicator for living with parents
- Access and utilization of health care, including mental health and maternal health
  - Indicator for receiving at least one antenatal care visit before time of survey
  - Indicator for having obtained care at a hospital ER in past six months
  - Indicator for receiving mental health treatment in the previous year
- Health behavior (e.g. drinking and smoking)
  - Indicator for reporting having consumed alcohol in the three months before pregnancy
  - Indicator for reporting having smoked cigarettes in the three months before pregnancy
- Psychological state/resources (measured on a PHQ-2 scale)
  - Indicator for PHQ-2 score of 3 or higher.
- Baseline measure of self-reported health
  - Indicator for self-reported health described as fair or poor.
- Maternal perceived stress level
  - Indicator for PSS-4 score of 4 or higher.
- Self-reported pregnancy risk factors

- Indicator for pre-pregnancy weight and height yielding BMI of normal.
- Family planning
  - Indicator for responding yes to having access to a place for family planning or birth control
  - Indicator for responding yes to wanting more children one day

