4.6.1. Describe study procedures for the nurse survey

Nurses will receive an email with a link to complete an online survey at a time that is convenient for them. Nurses will read the consent form and have an opportunity to email or call research staff regarding any questions before consenting to the survey. Everyone who consents to the survey will then be asked to complete the online survey.

Former NFP nurses who delivered NFP services at some point during the 2016-2020 period will receive a subset of questions to answer from the full survey.

4.7. Does the study involve the collection of data/specimens (including the use of existing data/specimens)?

No Yes: If yes; indicate how, when, where and from whom specimens or data will be obtained

NFP program staff will collect identifying information (including name, date of birth, social security number, address, and Medicare and Medicaid IDs (if applicable)) and baseline data (see draft baseline survey instrument attached) from study participants at intake, prior to randomization. The identifying information will be kept separate from the baseline survey responses. A unique code, not containing any identifying information, will be used to analyze participants’ baseline responses.

As explained to subjects in the Informed Consent documents, identifying information will be used to access historical and future administrative records that relate to the health and wellbeing of the mother and her children. This could include data on the birth of the mother’s children, health care use (such as how many times she or her children visit a health facility), government records, interaction with government services (such as cash assistance, food stamps, or child welfare), or from her children’s school after they start going to school. All of the information listed above is already collected about the mother and her children, even if they are not in the study. Taking part in the study means that the mother will allow our research team to use this existing secondary information for research purposes.

If a consented study participant is later discovered to be ineligible for the study/program (e.g. because she is over-income, not pregnant, or farther along in her pregnancy than she initially reported at study intake), the study team will continue to track and analyze administrative data for the participant and her children.

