Next, we will examine maternal experience of violence or homicide during the index pregnancy and during the first 24 months after the index birth using a combination of death records and Medicaid and hospital discharge data. This is defined as any record matching a code listed in

---

ii In our study protocol (McConnell et al 2020) we indicated that we planned to derive neonatal morbidity from discharge records. However, in order to make our analyses parallel with other analyses looking at neonatal morbidity (Han et al 2020) and because of concerns about the ability to translate these concepts directly into claims data (Ford et al 2007), we plan to rely instead on birth certificate data.

Table 1.2. As above, experience of violence was originally specified over 24 months, but we will explore analysis of this outcome during the index pregnancy because of the negative associations between exposure to maternal violence and birth outcomes. Our current definitions of substance abuse and maternal experience of violence are limited to the codes defined here; however, we will explore incorporating broader indicators of challenges with substance abuse derived from pharmacy claims, child claims, and criminal justice records. We will update these outcome specifications prior to any analysis of comparisons across treatment and control groups for these outcomes.

We will also examine use of social services during pregnancy and during the first 24 months after delivery. During pregnancy, we will examine any receipt of WIC benefits (derived from the birth certificate) and any receipt of Supplemental Nutrition Assistance Program (SNAP) benefits (from South Carolina Department of Social Services data). During the first 24 months after delivery, we will examine total months of receiving SNAP benefits and Temporary Assistance for Needy Families (TANF) benefits, as well as a measure of benefit churn, defined as receiving SNAP or TANF benefits at any time during a given year and having experienced at least one break in participation of four months or less that started and/or ended during the year.

Table 1.1. Codes for composite outcomes related to neonatal abstinence disorder and maternal drug/substance abuse

Code Description	ICD-10 Code(s)
Neonatal abstinence disorder	P96.1, P04*
Opioids	F11.*
Tobacco	F17.2*, O99.33*, Z72.0
Alcohol	V11.3*, F10.*
Sedative	F13.*
Cocaine	F14.*
Amphetamines	F15.*
Cannabis	F12.*

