#### Maternal utilization of mental health services

Analyses of outcomes related to maternal utilization of mental health services is also planned as a stand-alone analysis. NFP guidelines require nurses to screen for depression and anxiety at pre-specified intervals throughout the program, and to follow their agencies' protocols for referral and care coordination for women who screen positive. While directly measuring the

prevalence of depression and anxiety in our study sample would help us assess the impact of NFP on mental health, our study design relies exclusively on administrative data sources for outcome measurement. Therefore, our study design will seek to analyze how NFP changed the utilization of mental health services during the perinatal period.

We include all women with an index birth in our analytic sample, regardless of whether they had a prior mental health diagnosis before pregnancy. Because few women in our study are enrolled in Medicaid prior to pregnancy, we cannot observe prior diagnoses or identify treatment initiation. However, we expect rates of prior mental health diagnoses before pregnancy to be equal across treatment and control arms. Because the outpatient mental health treatment outcomes rely exclusively on Medicaid claims, we will restrict the analytic sample for outpatient outcomes to those women who retain full Medicaid coverage through 60 days postpartum. We will not restrict the sample for inpatient mental health outcomes as these rely on utilization that will be observable in all-payer hospital discharge data, regardless of payer.

While the medical definitions for depression and anxiety are distinct, we examine them together because they are comorbid conditions and NFP screens for them simultaneously. We define outpatient mental health treatment as a composite outcome of either a diagnosis for depression/anxiety/stress reaction or a filled prescription for antidepressants/anxiolytics or an outpatient psychotherapy visit during pregnancy or the first 60 days postpartum. We list the ICD-10 diagnosis codes, therapeutic class codes, and Current Procedure Terminology (CPT) codes used to define these outcomes in Tables 1.4, 1.5, and 1.6. Consistent with prior research, we consider all outpatient psychotherapy visits, including individual, family or group therapy to be mental health visits.

Table 1.4. Diagnosis codes for depression/anxiety/stress reaction

Code description	ICD-10 Code(s)

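### The single covariate set carries only pooled or self-reported stand-ins for prior benefit receipt and prior mental-health hospital use, which costs some precision on those secondary outcomes

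*SAP*

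**What the plan says.** SAP B.1 plans unadjusted models and also models that "adjust for characteristics at baseline that may be associated with our primary academic outcomes", all measured in the baseline survey. It then adds: "We plan to use the same set of control variables in all analyses".

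The covariates closest to the outcomes at issue are:

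- Benefits: "Indicator for receiving one or more social service (i.e. TANF, SNAP, SSI, unemployment benefits, and WIC", entered as one yes/no variable.
- Mental-health care: "Indicator for receiving mental health treatment in the previous year".
- Emergency care: "Indicator for having obtained care at a hospital ER in past six months", for any cause.
- Depressive symptoms: PHQ-2 of 3 or higher.

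The outcomes are more specific. In Addendum 1, the secondary-outcomes section (1.2.1) covers WIC receipt in pregnancy (from the birth certificate) and SNAP receipt in pregnancy (from Social Services data). For the 24 months after delivery, "we will examine total months of receiving SNAP benefits and Temporary Assistance for Needy Families (TANF) benefits", plus benefit churn. The mental-health section takes an indicator and a count of mental-health-related emergency or inpatient visits from hospital discharge data, from pregnancy to 12 months postpartum, and calls those data all-payer.

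On sources, Protocol section 4.7 says that "identifying information will be used to access historical and future administrative records". Section 4.7.1 lists Social Services and hospital encounter data matched to participants.

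**The concern.** The pre-randomisation value of a persistent outcome is often its best single predictor, and adjusting for it narrows the interval without introducing bias. A pooled any-service indicator gives the same value to a woman who has only WIC and a woman already on SNAP, so it predicts later SNAP months poorly. Likewise, any mental-health treatment and any ER visit only approximate a prior mental-health-coded hospital visit.

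Timing sharpens the point. Women enrol up to 27 weeks and 6 days of gestation (Protocol 4.4), while several outcome windows open at the start of pregnancy. A woman on SNAP at enrolment has already met the outcome of any SNAP receipt in pregnancy, so that part of the outcome cannot respond to treatment. The pooled indicator does not isolate it.

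What is at stake is the width of the intervals for a limited group of secondary outcomes.

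**Working it through.** **The plan's own figures.** The documents give no R-squared or precision figure for these outcomes. Protocol 5.2 covers primary outcomes only. Its birth-spacing power reproduces:

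- Effect: 0.14 × 0.18 × (0.95 − 0.05) = 0.0227.
- SE: 0.34 × √(1/2000 + 1/4000) = 0.0093.
- z = 2.44; power = Φ(2.44 − 1.96) = 0.68, against the stated figure of roughly 70%.

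The change considered here does not touch that figure. Eligibility requires no previous live birth, so birth, spacing and child outcomes have no prior value.

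**Starting precision for the secondary outcomes.** Addendum 4, Table 3 gives index-birth samples of 3,295 and 1,637. The detectable difference at 80% power, two-sided 0.05, is (1.96 + 0.84) × √(1/1637 + 1/3295) = 0.085, in units of the outcome SD left after the current adjustment.

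**Gain from a SNAP-specific baseline value.** Let p be the share on SNAP at baseline, q the share of the others with another listed service, and ρ the correlation between baseline SNAP and the outcome. All three are assumptions.

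- P(any service) = p + (1 − p)q
- Squared correlation of SNAP with the pooled indicator: k = p(1 − q) / P(any)
- R² with the pooled indicator alone: kρ². R² with SNAP added: ρ².
- SE ratio = √[(1 − ρ²) / (1 − kρ²)]

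Two corners bound the grid p = 0.2 to 0.4, q = 0.3 to 0.7:

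| | ρ = 0.3 | ρ = 0.5 | ρ = 0.7 |
|---|---|---|---|
| p = 0.4, q = 0.3 (k = 0.28/0.58 = 0.483): SE ratio | 0.975 | 0.924 | 0.817 |
| p = 0.2, q = 0.7 (k = 0.06/0.76 = 0.079): SE ratio | 0.957 | 0.875 | 0.728 |
| SE reduction, range | 2–4% | 8–13% | 18–27% |
| Detectable difference (SD), range | 0.083–0.081 | 0.078–0.074 | 0.069–0.062 |
| Power for an effect now at 80%, range | 82–83% | 86–89% | 93–97% |

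A simulation over the same grid agrees with these ratios to within about 0.002. Both ignore the other B.1 covariates (education, employment and so on), which would absorb part of the gain.

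**Gain for hospital mental-health visits.** Illustrative assumptions: 3% with a prior visit, 8% with the outcome overall, 40% risk among those with a prior visit.

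- Covariance = 0.03 × (0.40 − 0.08) = 0.0096
- r = 0.0096 / √(0.03 × 0.97 × 0.08 × 0.92) = 0.21
- SE reduction = 1 − √(1 − 0.043) = 2%

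That is before crediting the existing mental-health-treatment, ER and PHQ-2 covariates.

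**Where the missing values could come from.** The WIC outcome comes from the birth certificate, which holds no pre-enrolment series, so baseline WIC can come only from the survey. Protocol 4.7 permits use of historical records, but no start date is stated for the matched Social Services or hospital extracts. Separate survey indicators assume that the questionnaire recorded each programme; the pooled definition suggests it, but the instrument is not in the documents.

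**The case against.** One pre-specified set limits specification choice and keeps estimates comparable across many outcomes. It already holds proxies for benefits, mental-health treatment, ER use and depressive symptoms, so only the increment over these is lost. Randomisation protects the estimate, and unadjusted models are reported as well. All of this stands. It limits the point to efficiency but does not remove it, because the common set can stay and the addition can be fixed in advance for a named outcome family.

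A reader might infer more than the documents support:

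- *That prior benefit and mental-health status is left out altogether.* It is present in coarse form.
- *That the SAP gives a mistaken reason for omitting prior mental-health use.* The sentence "Because few women in our study are enrolled in Medicaid prior to pregnancy, we cannot observe prior diagnoses or identify treatment initiation" explains why women are included regardless of prior diagnosis. It concerns the sample definition and does not argue against a covariate.
- *That twelve earlier months of every outcome are already in hand.* Permission to use historical records does not show that the matched extracts reach back that far. The encounter file dated 2010–2014 is public-use, the Social Services file described as historical is de-identified, and the matched encounter agreement names child injury as its purpose.
- *That a large gain is established.* Every correlation above is assumed.

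**Conclusion.** The point holds as a modest efficiency issue. A set chosen for the primary outcomes is applied to secondary outcomes whose own baseline value it represents only through a pooled indicator or self-reported proxies. There is no bias, and the primary results do not change.

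For SNAP-type outcomes the standard error would fall by roughly 2% to 27% beyond the pooled indicator. This rests on assumed correlations of 0.3 to 0.7, SNAP prevalence of 20% to 40% and other-service prevalence of 30% to 70%. Outcomes whose window opens before enrolment may lie towards the upper end. For uncommon mental-health hospital visits the gain may be only a few percent. The documents do not allow a narrower statement.

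**What to change.** Keep the common set and add to B.1:

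1. Social-service outcomes are adjusted for separate baseline-survey indicators of SNAP, TANF and WIC in place of the pooled indicator.
2. Where the matched Social Services and all-payer hospital extracts reach back before enrolment, add prior months on SNAP/TANF for the social-service outcomes and any prior mental-health-coded emergency or inpatient visit for the hospital mental-health outcomes. Measure these strictly before the enrolment date, and state the look-back window.
3. Use the B.2 missing-indicator method for unmatched women.

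The cost is SAP wording, a check of the extract start dates and, where they allow, some additional months of data. Covariate lists would differ slightly between outcome families.

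Addendum 4 (February 2025) describes the trial manuscripts, including those on mental health and social services, as published or forthcoming. For any analysis already run, report the change as a dated post hoc sensitivity analysis beside the pre-specified model.

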### **B.2. Missing values of control variables**

We will treat baseline responses as missing if sample members responded to questions with "Don't know" or "Refused to Answer." We will use the dummy-variable adjustment method to account for missing baseline covariates in our analysis. Specifically, we will set missing covariate values to a constant value and add indicators (i.e., dummy variables) for missing values to the impact analysis model. We will also assess our results' robustness to a model specification without baseline covariates. Finally, based on the prevalence and patterns of missing covariate data, we may specify a multiple imputation model to impute missing values.

### **B.3. Alternate Empirical Specifications**

Per McConnell et al. (2020), we will estimate intent-to-treat (ITT) effects as our primary empirical specification. We may also consider secondary specifications that incorporate data on actual program participation, taking advantage of the randomization as an instrument for participation to estimate local average treatment effects and to examine average characteristics of those participating in the program. We anticipate that the primary alternative definitions of interest for program participation will be based on reaching the milestone of participating in home visiting through the period surrounding the expected delivery date, the child's first birthday and the child's second birthday. We would operationalize participation through the expected delivery date and the child's first birthday as mothers who receive a nurse visit within 14 days of the milestone. Participation through the child's second birthday would be operationalized as a visit within 1 month (31 days) of the milestone. In accordance with the NFP program model, mothers should receive a visit approximately once every two weeks in the period leading up to delivery through the first 21 months of the child's life and should receive a visit once every month in months 21-24 of the child's life.

## **Nurse-Family Partnership Evaluation Analysis Plan Addendum 1: Pregnancy, Birth and Maternal Health Outcomes.**

*Note: This version of Addendum 1 reflects plans for study design as of January 20, 2021.*

The goal of this analysis plan addendum is to enumerate analysis specific to the pregnancy, birth, and maternal health outcomes domain.

### **1. Methods**

A full treatment of our empirical approach, primary study outcomes, planned subgroup analyses, and statistical power is given in sections 2.4-2.10 of McConnell et al. (2020). The following sections provide additional context and details on planned analyses for the pregnancy, birth, and maternal health outcomes domain of the NFP evaluation.

